#### 14.5 Summary of baseline data and flow of participants

Baseline characteristics and clinical data for randomised patients will be summarised but not subjected to statistical testing. All participating sites will be asked to keep a log of consented patients who were screen failures. Reasons for non-participation will be categorised and summarised. Participation in the trial, treatment allocation and completeness of follow-up will be illustrated by a CONSORT flow diagram.

#### 14.6 Analysis of participant populations

For the purposes of the analyses, the following analysis populations are defined.

Randomized population includes all participants who were randomized to the study.

**Safety population** includes all participants who were randomized and received at least 1 dose of study drug. Safety population will be used for safety analysis. If a participant received study drug dose different from the one to which the participant was randomized, the participant's safety data will be analysed as treated.

**Intention-to-treat (ITT) population** includes all participants who were randomized and received at least 1 dose of study drug during the Induction Period. ITT population will be used for efficacy analysis. If a participant received a study drug dose different from the one to which the participant was randomized, the participant's efficacy analyses will be performed as randomized.

**ITT-Maintenance population** includes all participants who were randomized and received at least 1 dose of study drug in Maintenance Period. If a participant received study drug dose different from the one to which the participant was randomized, the participant's efficacy data will be analysed as randomized.

**Pharmacokinetic (PK) population** includes all participants who were randomized, received at least 1 dose, and have any evaluable plasma concentration of study drug.

**Biomarker population** includes all participants who were randomised, received at least 1 dose of study drug, and have any evaluable measurement of biomarker of interest.

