All patients with sufficient RNA for analysis will be stratified according to the biopsy result and will be randomised (1:1 allocation ratio) into the abatacept arm or the placebo arm.

Randomisation procedures are detailed in the 3TR-PARTNER-RA Trial Randomisation Specification form.

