#### 7.6.12 Pre & Post Biopsy Questionnaire

Prior to and following the biopsy procedure, patients & clinicians will complete pre and post biopsy questionnaires. The pre and post-biopsy questionnaires are developed by EMR to collect information on the safety and tolerability of the synovial biopsy procedure. A standard questionnaire will be administered to all patients immediately pre-biopsy and at the subsequent visit post-biopsy. Patients indicate pain, swelling and stiffness of the biopsied joint pre and post procedure using a visual analogue score (VAS). In the post-biopsy questionnaire patients were also asked to record the level of pain or discomfort suffered during the procedure, additional analgesics taken, and specific adverse events of interest are recorded.

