## 8.0 Participant, Study, and Site discontinuation

#### 8.1 Subject Withdrawal from Study/Withdrawal of Consent

Patients who consent to the study but do not undergo synovial biopsy at visit 2 will be withdrawn from the study. Additionally, patients who have a biopsy sample with insufficient RNA for Nanostring analysis will be withdrawn from further participation in the trial. This should be communicated to the patient by the principal investigator or delegated clinician, and patients will receive treatment as per routine care.

Participants may cease randomised treatment and/or be withdrawn from the study if they no longer fulfil the participation criteria, at physician's discretion. Subjects may also withdrawn consent for any reason at any time without prejudice to their normal care or may be withdrawn at any time at the discretion of the investigator for safety, behavioural or administrative reasons. Samples collected prior to withdrawal will be kept unless the patient specifically requests otherwise. The PIS will make clear to participants that data collected prior to withdrawal will be kept and their rights to destroy this data are limited.

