## 14.0 Statistical and data analysis

#### 14.1 Sample size calculation

The primary analysis of the trial is the comparison between Group 1 and Group 3 (see figure in Section 2.6), i.e. the patients classified as biomarker positive treated with Abatacept + Methotrexate (MTX) (Group 1) vs. the patients classified as biomarker negative treated with Abatacept + Methotrexate (MTX) (Group 3). Since patients will be randomised 1:1 to either Abatacept + MTX or Placebo + MTX and the median value observed in the PEAC study as a cut-off to classify the biomarker status, we expect the comparison groups to be roughly equal. That would allow to ascribe the differences in response we will observe to the different biomarker profiles of the two groups, hence demonstrating if the presence of a biomarker will enhance the response to the any of the drugs included in the trial.

The power calculation is done for this comparison, based on the following assumptions:

50% patients will be classified as biomarker positive and 50% as biomarker negative
 Using change in CDAI score from baseline (delta CDAI) as the primary outcome, a difference in delta CDAI between the two comparison groups of 10, with a Standard Deviation of 14.34. These are the values that were observed when analysing the difference in delta CDAI between biomarker positive and biomarker negative patients treated with MTX in the PEAC study. Although PEAC patients were not treated with Abatacept, this comparison is expected to be even more in favour of the biomarker positive group using Abatacept together with MTX. Thus, basing the power calculation on the PEAC observed difference is a conservative assumption.

With these assumptions, 88 patients would be needed to detect a significant difference of 10 in delta CDAI with 90% power (66 patients for 80% power). Since this would only be for Group 1 and Group 3 (44 patients each), a total of 176 patients would be sufficient for 90% power in the whole trial (132 for 80% power) which includes all four groups as per Figure 1 Section 2.6. If we assume a 5% dropout rate and also account for an expected 5% of patients that have insufficient RNA for the Nano-string analysis (based on results from the STRAP trial), 196 patients in the whole trial would be sufficient to detect a significant difference (Group 1 vs Group 3) of 10 in delta CDAI with 90% power (147 patients for 80% power).

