#### 14.9 Safety analysis

The safety analysis set consists of patients who received at least one dose of the trial medication. Safety analysis will be based on the safety analysis set. All AEs will be recorded, notified, assessed for seriousness, and severity, reported, analysed and managed in accordance with the Medicines for Human Use (Clinical Trials) Regulations 2004. The reporting and notification of serious adverse events (SAEs) and suspected unexpected serious adverse reactions (SUSARs) is specified in the protocol and these events will be summarised by treatment and pathotype.

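### Patients withdrawn for insufficient RNA after the mandatory biopsy have no scheduled post-biopsy form or adverse event check, and their biopsy events have no place in the safety analysis

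*Protocol*

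**What the plan says.** **The biopsy.** Section 7.6.16 makes the visit 2 synovial biopsy mandatory. Section 1.3 says such biopsies are not usually part of routine care and lists infection, bleeding, pain, swelling and damage to surrounding tissue as possible risks.

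**The forms.** Section 7.6.12 says that the pre- and post-biopsy questionnaires exist to "collect information on the safety and tolerability of the synovial biopsy procedure". It fixes who completes them and when: "A standard questionnaire will be administered to all patients immediately pre-biopsy and at the subsequent visit post-biopsy". Section 7.5.3 and the schedule in 7.2 place the post-biopsy form at visit 3, the baseline visit at which treatment starts.

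**Who leaves in between.** Only patients with sufficient RNA are randomised (7.3). Section 8.1 says that "patients who have a biopsy sample with insufficient RNA for Nanostring analysis will be withdrawn from further participation in the trial". Section 14.1 puts a figure on this; its inflation is meant to "also account for an expected 5% of patients that have insufficient RNA".

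**Who is analysed for safety.** In section 14.6 the Safety population "includes all participants who were randomized and received at least 1 dose of study drug. Safety population will be used for safety analysis". Section 14.9 repeats the dose requirement: "The safety analysis set consists of patients who received at least one dose of the trial medication". On SAEs and SUSARs it adds that "these events will be summarised by treatment and pathotype".

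**The concern.** Section 7.6.12 sets out to collect the form from all patients, but ties it to a visit that some biopsied patients are withdrawn too early to attend. The two statements cannot both be carried out. Patients with insufficient RNA have undergone an invasive procedure for the trial and receive no trial treatment. They are also the group from whom the plan schedules no structured information on how the procedure went.

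The analysis side adds to this. Any biopsy event such a patient reports falls outside a safety set that requires randomisation and a dose, and there is no treatment arm to tabulate it under. A summary of biopsy harms drawn from the defined set would rest on fewer patients than were biopsied.

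The collection gap is the more important half. A statistical analysis plan can add an analysis set later, but it cannot recover a form or an adverse event check that was never taken.

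**Working it through.** **1. The plan's own figures (14.1).** Inputs: difference 10, SD 14.34, power 90% or 80%. The significance level is not given there; two-sided 5% is assumed.

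- n per group = 2 × (z₁₋α/₂ + z₁₋β)² × (SD/difference)², normal approximation.
- 90% power: 2 × (1.960 + 1.282)² × 1.434² ≈ 43.2, so 44 per group, 88 for Groups 1 and 3, and 176 for four groups. This matches.
- 80% power: 2 × (1.960 + 0.842)² × 1.434² ≈ 32.3, so 33 per group, 66 and 132. This matches.
- Inflation for 5% dropout and 5% insufficient RNA: 176 / 0.90 = 195.6, so 196. Applying the two losses in turn, 176 / 0.95² = 195.01, also 196. At 80% power, 132 / 0.90 = 146.7, so 147. This matches.

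**2. How many biopsied patients are affected.** The 5% comes from 14.1. The synopsis gives 200 randomised patients, while 3.1 speaks of recruiting 200, so both readings are shown.

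| Basis | Biopsied | Insufficient RNA |
|---|---|---|
| 196 biopsied | 196 | 196 × 0.05 = 9.8 |
| 200 biopsied | 200 | 200 × 0.05 = 10 |
| 200 randomised | 200 / 0.95 = 210.5 | 10.5, about 11 |

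At most about 186 of 196, or 190 of 200, could then enter a dosed-only set. If the failure rate were anywhere from 2% to 15% (an assumed range), the number would run from about 4 (196 × 0.02 = 3.9) to about 35 (200 / 0.85 − 200 = 35.3). Patients who leave for other reasons between biopsy and first dose add to this; the protocol gives no figure for them.

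**3. Does any other scheduled step reach these patients?**

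- Visit 2 adverse event check (7.5.2): it appears in a list headed as recorded before the biopsy. That list also contains the biopsy and randomisation, so its order should not be read literally. Even so, a check on the day of the procedure is not the follow-up that 7.6.12 places at the next visit.
- End of adverse event reporting (12.4): tied to the patient's time on the trial and to the week 16 visit or last dose. An undosed patient has no such dosing or week 16 anchor.
- Withdrawal procedure (8.2): the return visit at week 16 is for patients who stop randomised treatment. For others there is a withdrawal CRF with a reason, but no post-biopsy form.
- Telephone completion of the form (7.5.4): written only for the optional week 16 biopsy.
- Analysis populations (14.6): every one listed requires randomisation.

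None of these steps schedules the form or a post-biopsy adverse event check for a patient withdrawn for insufficient RNA.

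**The case against.** The strongest reply is that a safety set of dosed patients, analysed as treated, is the usual one for drug safety, and that a further set for a procedure can be left to the statistical analysis plan. The first part stands: the definitions in 14.6 and 14.9 are not wrong for their purpose. The second part answers only the analysis half, because the missing form is fixed by the protocol's visit structure.

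A reader might infer that these patients disappear from the harm data altogether. The protocol does not support that. Adverse events are recordable from screening, and patients are told to report events outside scheduled visits (12.4). SAEs go to the sponsor within 24 hours (12.6) and to the manufacturer from consent onwards (12.6.1). The annual safety report weighs all events arising on the study (13.1). Serious biopsy harm in such a patient would therefore be recorded and reported.

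A reader might also infer that the trial will publish a biopsy complication rate that is too low, because insufficient RNA marks the difficult procedures. The protocol plans no such rate: it is not among the objectives or endpoints in section 2, and section 14 plans no analysis of the questionnaires. Nothing links RNA failure to complications either. Samples are shipped, extracted and quality-checked before assay (7.6.16 and the laboratory parts of section 9), so failure may have nothing to do with how the biopsy went. Any figure for bias would rest on invented event rates.

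**Conclusion.** The point holds as a small gap in data collection, with a matching gap in the analysis. Followed as written, the plan takes no post-biopsy form and schedules no post-biopsy adverse event check for about 10 of 196 to 200 biopsied patients (about 11 if 200 are randomised), plus an unstated number who leave before dosing for other reasons. Biopsy events they do report have no defined set to be summarised in.

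The count rests on the protocol's expected 5% RNA failure; the rest follows from the text. The direction and size of any effect on a biopsy event rate are unknown, and no figure should be quoted. The drug Safety population is not in error. Priority is low: nothing in the efficacy or drug safety analyses changes. The correction is still worth making because it is cheap and concerns an invasive procedure outside routine care.

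**What to change.** - **7.6.12 and 8.1 to 8.2:** require the post-biopsy form and an adverse event check, by telephone if needed, from any biopsied patient who is withdrawn for insufficient RNA or leaves before the first dose. For RNA failures the occasion already exists, since 7.6.16 and 8.1 have the investigator or a delegated clinician tell the patient. This extends to the visit 2 biopsy the telephone option that 7.5.4 gives for the week 16 biopsy.
- **14.9:** add that biopsy-related adverse events and the pre- and post-biopsy forms are summarised descriptively over all patients in whom a biopsy was attempted, separately from the drug Safety population, which stays as defined.

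The cost is about 10 short contacts and one extra descriptive table.

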#### 14.7 Primary endpoint analysis

The primary analysis is within the abatacept arm. It will assess the difference in the change in Clinical Disease Activity Index (CDAI) score at 16 weeks between the biomarker positive and the biomarker negative patients (i.e. Group 1 vs Group 3). This analysis will be on an ITT basis according to original randomisation allocation. The primary outcome will be analysed by analysis of covariance (ANCOVA) with treatment as a factor and baseline value as continuous covariate. If assumptions for ANCOVA are not met, non-parametric ANCOVA will be used. The treatment effect will be reported as least squares mean with 95% confidence intervals.

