The randomized intervention kit number list is generated centrally by BMS and IMPs are packaged in accordance with this list. The randomization and intervention allocation are performed centrally by the Early RA 3TR Database, which generates the participant randomization list and allocates the intervention number and the corresponding intervention kits to the participants according to it.

A randomized participant is defined as a participant who has been allocated to a randomized intervention regardless of whether the intervention kit was used or not (ie, participants registered by the Early RA 3TR Database in the 3TR-PARTNER-RA study). A participant cannot be randomized more than once in the study.

The result (i.e. randomised treatment arm) will then be filled to the local site staff (each site will have a nominated joint assessor). The local site staff will immediately be able to see the result of the randomisation, however, they will be blinded to any information about the patient's biopsy result.

Randomisation methods and procedures will be described within the Database User Manuals and Data Management Plan.

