#### 14.4 Statistical Analysis

The statistical analysis of the trial will be described in detail in the Statistical Analysis Plan (SAP). This will be finalised prior to the analysis of the data. In brief, the primary outcome, which is a continuous outcome, will be analysed by analysis of covariance (ANCOVA) with treatment as a factor and baseline value as continuous covariate. If assumptions for ANCOVA are not met, non-parametric ANCOVA will be used. Changes from baseline within groups will be analysed with a paired Wilcoxon test. Secondary binary endpoints will be analysed using a  $\chi^2$  test unless any element within the contingency table has fewer than 5 individuals in which case a Fisher's exact test will be used.

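### The primary ANCOVA names treatment as its factor, but treatment is constant in the abatacept-only comparison and no biomarker term is stated, so the model as written cannot estimate Group 1 vs Group 3

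*Protocol*

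**What the plan says.** Section 14.7 sets the scope first: "The primary analysis is within the abatacept arm". It gives the contrast as the difference in change in CDAI at 16 weeks "between the biomarker positive and the biomarker negative patients (i.e. Group 1 vs Group 3"). Sections 2.1 and 14.1 name the same contrast, and 14.1 powers the trial for it.

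The model follows in 14.7: "The primary outcome will be analysed by analysis of covariance (ANCOVA) with treatment as a factor and baseline value as continuous covariate". The reporting rule is "The treatment effect will be reported as least squares mean with 95% confidence intervals". Section 14.4 gives the same model in its summary, where the primary outcome "will be analysed by analysis of covariance (ANCOVA) with treatment as a factor and baseline value as continuous covariate". Neither section names a biomarker term. The non-parametric fallback in both sections names no other factor, and 14.8 repeats the primary analysis on the secondary endpoints.

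On the analysis set, 14.7 says: "This analysis will be on an ITT basis according to original randomisation allocation". Section 14.6 defines the ITT population as one that "includes all participants who were randomized and received at least 1 dose of study drug during the Induction Period", and assigns that population to the efficacy analysis. Section 7.3 counts a participant as randomised "regardless of whether the intervention kit was used or not".

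**The concern.** An ANCOVA estimates differences between levels of its factor. Here the analysis has been restricted to a single level of the factor that is named. The variable that separates the two groups, biomarker status, is not in the model. The label given to the result, a treatment effect, describes something that cannot exist inside one treatment arm.

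This is the one comparison the trial is powered for. The protocol does not leave the factor to the SAP; it states one, and it is the wrong one. A SAP that follows the protocol inherits a model that cannot be fitted for its purpose, and a SAP that names biomarker status departs from the protocol's text. The continuous secondary endpoints (HAQ-DI and SF-36) take over the same wording through 14.8.

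The population text raises a smaller question. The ITT definition depends on a trial period that is not defined, and its dosing requirement does not match the ITT claim in 14.7.

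**Working it through.** **1. The plan's own sample size.** Inputs from 14.1: difference 10, SD 14.34, 50/50 biomarker split, 1:1 allocation, and 5% dropout plus 5% insufficient RNA. Alpha is not stated there; two-sided 0.05 is assumed, in line with the 95% intervals in 14.7.

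n per group = 2 × (z₁₋α/₂ + z₁₋β)² × SD² / difference²

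- 90% power: 2 × (1.960 + 1.282)² × 14.34² / 10² ≈ 43.2, rounded up to 44. Two groups: 88. Four groups: 176. 176 / 0.90 = 195.6, giving 196.
- 80% power: 2 × (1.960 + 0.842)² × 14.34² / 10² ≈ 32.3, rounded up to 33. Two groups: 66. Four groups: 132. 132 / 0.90 = 146.7, giving 147.

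All six figures in 14.1 are reproduced. One-sided 0.05 would give 72 and 52 for the two-group comparison, so it does not match. The calculation is for a two-group biomarker comparison, which is not the model that 14.7 states.

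**2. The model as written, abatacept arm only.** Take 44 + 44 patients and the columns intercept, treatment, baseline CDAI. Treatment is 1 for all 88 patients, so its column equals the intercept column. Rank: 2 of 3. The treatment coefficient is not estimable.

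A least squares mean for the single level can still be computed, but at the mean baseline it is only the overall mean change in the arm. With mean changes a₁ and a₃ in Groups 1 and 3, that is (44a₁ + 44a₃) / 88 = (a₁ + a₃) / 2. This says nothing about a₁ − a₃, which is the primary result.

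**3. The same model on all four groups.** With 176 patients the treatment-only model has rank 3 of 3, but the biomarker contrast is still not among the quantities it can estimate. Its coefficient is abatacept minus placebo.

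**4. The model with biomarker status as factor, abatacept arm only.** Columns intercept, biomarker, baseline CDAI. Rank: 3 of 3. The biomarker coefficient is the adjusted Group 1 minus Group 3 difference.

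**5. Effect of the correction on power.** At 44 per group, power is 90.5% (normal approximation) or 89.9% (t-test) if baseline explains no variance. The protocol gives no correlation with baseline. If baseline is assumed to explain 10%, 25% or 40% of the variance, power is about 93%, 96% or 99%. N does not change.

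**6. The analysis set.**
- Sections 2.6 and 7.2 describe one treatment phase from week 0 to week 16. No induction or maintenance period is defined. The only other use of the term Induction Period is in section 1.1, for a cited abatacept study in methotrexate-naive early RA.
- The PK set in 14.6 needs plasma drug concentrations, which appear in neither the objectives, the endpoints nor the schedule. No analysis in section 14 uses the Maintenance or PK set.
- Section 14.6 drops randomised but undosed participants from the set it calls ITT, while 14.7 claims ITT by original allocation.
- Biomarker status is not randomised. Original allocation therefore settles who is in the abatacept arm, but not which of the two compared groups a participant belongs to.

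**The case against.** The strongest reply is that nobody could mistake the intention. Section 14.7 states the contrast before it gives the model, and 2.1 and 14.1 agree with it. Arm, endpoint, time point, groups, covariate and method are all fixed, and only one variable separates Group 1 from Group 3. Section 14.4 describes its text as brief and defers detail to a SAP, which is not at hand and may already name the factor. All of this stands. It limits the consequence, but it does not make the stated model correct, and the error appears in two sections and again in the name given to the result.

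A reader might infer more than the protocol supports:

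- That the primary analysis would answer abatacept vs placebo instead. That requires adding the placebo arm, which 14.7 excludes.
- That the ITT wording helps make the contrast inestimable. It does not; the factor alone does that.
- That no participant can belong to the ITT set. With one treatment phase, the workable reading is at least one dose of study drug, as in the Safety definition.
- That up to three weeks separate randomisation from first dose. Three weeks is the outer limit from biopsy to baseline (7.5.2). Randomisation waits for the biopsy result (7.3), and section 1.2 expects profiling within 7–10 working days, so the gap should usually be shorter. The protocol gives no number of participants lost in it.
- That the repair must come after outcomes are known. Section 14.4 only requires the SAP to be final before the analysis, and with one possible factor there is little room for a data-driven choice.

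On the dosing requirement, 14.6 keeps a separate Randomized population, so 7.3 is not contradicted outright. Because the primary contrast is not a randomised one, leaving out undosed patients does not break a randomised comparison there. What remains is that the label and the claim in 14.7 do not match the definition.

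**Conclusion.** The point holds as a specification error in the primary analysis. As written in 14.4 and 14.7, the model has a factor with one level (rank 2 of 3) and no term for the primary contrast, so it cannot produce the Group 1 vs Group 3 difference. This follows from the text and needs no numerical assumption. The estimand is not in doubt, the sample size is unaffected, and wording alone corrects the model. It should be corrected because it is the confirmatory analysis and the protocol text is what a SAP will be checked against.

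The ITT definition is a second, lesser defect: leftover reference to a period this trial lacks, and a dosing condition at odds with 14.7. The Maintenance and PK sets are unused text with no effect on the primary result.

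**What to change.** - **14.4 and 14.7:** name biomarker status (positive/negative) as the ANCOVA factor within the abatacept arm, with baseline CDAI as the continuous covariate. Use the same factor in the non-parametric fallback. Replace the reference to a treatment effect with the adjusted biomarker difference in week-16 change in CDAI and its 95% CI.
- **14.6:** remove the Induction Period wording and make the set agree with 14.7. Either define ITT as all randomised participants, by allocated arm and baseline biomarker class, or keep the dosing condition and give that set another name. If all randomised participants are kept, say how those with no CDAI from the baseline visit are handled.
- **14.6:** delete the Maintenance and PK sets.

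The contrast described in 14.8 is stated correctly. It covers binary and continuous endpoints, so no single formula with baseline CDAI would serve all of them; those models can be left to the SAP.

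Cost: a few sentences, before the SAP is finalised. Sample size, visits and data collection do not change.
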